5.3 SAMPLE STORAGE, TRACKING AND DISPOSITION

Samples will be ordered in CRIS and tracked through a Clinical Trial Data Management system. Should a CRIS screen not be available, the CRIS downtime procedures will be followed. Samples will not be sent outside NIH without appropriate approvals and/or agreements, if required.

5.3.1 Clinical Pharmacology Program

Upon arrival in the Clinical Pharmacology Program (CPP), OCD, CCR, NCI, all samples are barcoded, with data entered and stored in Labmatrix, the system utilized by the CPP. This is a secure program, with access to the Labmatrix system limited to defined CPP personnel, who are issued individual user accounts. Labmatrix creates a unique barcode ID for every sample and sample box, which cannot be traced back to patients without Labmatrix access. The data recorded for each sample includes the patient ID, name, trial name/protocol number, time drawn, cycle, time point, dose, material type, as well as box and freezer location. There are patient demographics that can be obtained to correlate with the samples through Labmatrix. For each sample, there are notes associated with processing method (delay in sample processing, storage conditions on the ward, etc.)

Barcoded samples are stored in barcoded boxes in a locked freezer at either -20°C or -80°C according to stability requirements. These freezers are located onsite in the CPP and offsite at NCI Frederick Central Repository Services in Frederick, MD. Samples will be stored until requested by the researcher assigned to the protocol. All requests are monitored and tracked in Labmatrix. All researchers are required to sign a form stating that the samples are only to be used for research purposes associated with this trial (as per IRB approved protocol) and that any unused samples must be returned to the CPP.

Following completion of this study, samples will remain in storage as detailed above. Access to these samples will only be granted following IRB approval of an additional protocol, granting the rights to use the material.

5.3.2 Leidos Biomedical, Inc. Lab

Blood and tissue collected during the course of this study will follow storage, handling and labeling procedures to ensure that security, confidentiality and sample integrity are maintained. All samples (blood or tissue) are tracked by distinct identification labels that include a unique patient identifier and date of specimen collection. Thus, samples will be de-identified of personal data, with access to personal data restricted to the study investigators.

All cryopreserved samples are tracked for freezer location and storage criteria. All Samples are stored in a locked freezer at -70°C according to stability requirements. These freezers are located offsite at NCI-Frederick, at the Leidos Biomedical, Inc. Lab in Frederick, MD. Samples will be stored until requested by a researcher named on the protocol. All use and requests for use will be recorded by the Leidos Biomedical, Inc. Lab. Any unused samples must be returned.

Some samples as indicated below may be stored in monitored freezers/refrigerators in the investigator's laboratory at specified temperatures with alarm systems in place.

At the termination of this protocol, samples will remain in storage as detailed above. If additional studies are to be performed on any samples retaining patient identifiers, obtained during the conduct of this trial, a Request to Conduct Research for Stored Human Samples Specimens, or Data Collected in a Terminated NCI-IRB Protocol will be submitted. Otherwise, access to these samples will only be granted following IRB approval of an additional protocol, granting the rights to use the material. If specimens are to be discarded at any point, they will be disposed of in accordance with the environmental protection laws, regulations and guidelines of the Federal Government and the State of Maryland.

If, at any time, a patient withdraws from the study and does not wish for their existing samples to be utilized, the individual must provide a written request. Following receipt of this request, the samples will be destroyed (or returned to the patient, if so requested). The PI will report any loss or unanticipated destruction of samples per Section 7.2.

5.3.3 Laboratory of [name]

Samples will be processed immediately by the [name] laboratory. Biospecimens will be collected and processed using validated SOPs that will ensure both specimen quality and patient confidentiality. Using a computerized inventory system and a backup hardcopy process, all specimen collection and processing steps will be documented, and the specific location of each specimen will be tracked. Each new specimen collected will be assigned a unique barcode identifier that can be linked to the original specimen collected and other relevant information within the inventory system. Specimen labels will indicate protocol number, order in which the patient enrolled on the trial, type of sample, collection time, and total volume collected, as appropriate. The inventory process contains other security provisions sufficient to safeguard patient privacy and confidentiality. Access to the inventory system and associated documents will be restricted to appropriate individuals. Requests to use specimens stored in the repository must be approved. SOPs ensure that any changes in informed consent made by a patient and relayed to the PI will be reflected in the inventory system to ensure that specimens are destroyed as appropriate. All laboratory personnel will be trained to adhere to SOPs and will be monitored for high-quality performance.

5.3.4 Protocol Completion/Sample Destruction

All specimens obtained in the protocol are used as defined in the protocol. Any specimens remaining at the completion of the protocol will be stored in the conditions described above. The study will remain open as long as sample or data analysis continues. Samples from consenting subjects will be stored until they are no longer of scientific value or until a subject withdraws consent for their continued use, at which time they will be destroyed. Once primary research objectives for the protocol are achieved, intramural researchers can request access to remaining

samples, provided they have an IRB-approved protocol and participant consent or an exemption from OHSRP.

The PI will record any loss or unanticipated destruction of samples as a deviation. Reporting will be per the requirements of Section 7.2.

5.3.5 NCI Laboratory of Pathology

Tissues designated for clinical diagnostics are transported to the Laboratory of Pathology (LP) where they are examined grossly, and relevant portions are fixed, embedded in paraffin and sectioned and stained for diagnostic interpretation. Unutilized excess tissue that is not placed in paraffin blocks is stored in formalin for up to three months, in accordance with College of American Pathologists/Joint Commission on Accreditation of Healthcare Organizations (CAP/JCAHO) guidelines, and then discarded. Following completion of the diagnostic workup, the slides and tissue blocks are stored indefinitely in the LP's clinical archives. All specimens are catalogued and retrieved utilizing the clinical laboratory information systems, in accordance with CAP/JCAHO regulations. The use of any stored specimens for research purposes is only allowed when the appropriate IRB approval has been obtained. In some cases, this approval has been obtained via the original protocol on which the patient was enrolled.

6 DATA COLLECTION AND EVALUATION

6.1 DATA COLLECTION

The PI will be responsible for overseeing entry of data into an in-house password protected electronic system (C3D and Labmatrix databases) and ensuring data accuracy, consistency and timeliness. The principal investigator, associate investigators/research nurses and/or a contracted data manager will assist with the data management efforts. All data obtained during the conduct of the protocol will be kept in secure network drives or in approved alternative sites that comply with NIH security standards. Primary and final analyzed data will have identifiers so that research data can be attributed to an individual human subject participant.

All adverse events, including clinically significant abnormal findings on laboratory evaluations, regardless of severity, will be followed until return to baseline or stabilization of event.

Document AEs from the first study intervention, Study Day 1, through the end of the treatment. After 30 days, only adverse events which are serious and related to the study intervention need to be recorded.

An abnormal laboratory value will be recorded in the database as an AE **only** if the laboratory abnormality is characterized by any of the following:

- Results in discontinuation from the study
- Is associated with clinical signs or symptoms
- Requires treatment or any other therapeutic intervention
- Is associated with death or another serious adverse event, including hospitalization.
- Is judged by the Investigator to be of significant clinical impact

• If any abnormal laboratory result is considered clinically significant, the investigator will provide details about the action taken with respect to the test drug and about the patient's outcome.

End of study procedures: Data will be stored according to HHS, FDA regulations, and NIH Intramural Records Retention Schedule as applicable.

Loss or destruction of data: Should we become aware that a major breach in our plan to protect subject confidentiality and trial data has occurred, this will be reported expeditiously per requirements in Section 7.2.1.

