Renal toxicity	In the event of Grade 1 or greater renal toxicity consider increasing oral or intravenous hydration, and consider delaying LMB-100 administration by up to 48hrs.			
	In the event of Grade 2 or greater renal toxicity hold LMB-100 administration until recovery to Grade 1 or better. If this does not occur within 48hrs, no further LMB-100 should be given during the cycle.			
IRR = infusion related reaction; IV =	= intravenous; CTCAE = Common Terminology Criteria for Adverse			

Events

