10.1.2 Secondary Endpoints

The secondary endpoints for both the dose expansion and dose escalation cohorts are the LMB-100 peak serum level, half-life and AUC during cycle 1, and the percentage of participants with EOI LMB-100 serum drug concentration that meets threshold during cycle 3. For the dose escalation cohort, the percentage of participants with EOI LMB-100 serum drug concentration that meets threshold during cycle 2 of treatment will also be measured. For the dose expansion cohort, the number and description of adverse events by grade will also be reported.

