10.4.4 Safety Analyses

Safety will be evaluated during the dose escalation phase and will include reporting toxicities by grade and type at each dose level in addition to DLTs.

During the 15-patient expansion cohort, the following rule will be used: Within the initial 6 patients, no more than 1 patient in 6 is permitted to experience a DLT attributable to study agents. After the initial 6 patients, safety will be monitored continuously per the following rule: if the cumulative fraction of patients enrolled who experience a DLT attributable to study agents is 1/6 or less, patients will be allowed to continue to enroll onto this protocol.

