12.1.2.5 Risk of Renal Toxicity

LMB-100 administration may cause renal toxicity characterized by increased creatinine, BUN, and proteinuria. In preclinical cynomolgus monkey studies, LMB-100 has shown increases in creatinine and histological changes including regenerative and degenerative changes to the tubular epithelium. Hemolytic uremic syndrome has been reported for other cytolytic fusion antibodies in development.

Participants should be monitored with renal laboratory assessments including creatinine, BUN, and urinalysis.

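### Graded laboratory changes without symptoms, treatment or judged importance may be missing from the safety results: 6.1 has no grade or drug-hold criterion, and Section 10 plans no laboratory summary

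*Combined protocol and SAP*

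**What the plan says.** Section 6.1 sets the recording rule: "An abnormal laboratory value will be recorded in the database as an AE" only if at least one of five conditions holds. Three of them are "Results in discontinuation from the study", "Is associated with clinical signs or symptoms" and "Requires treatment or any other therapeutic intervention". The other two are association with a death or another SAE (hospitalization included) and the investigator's judgement that the clinical impact is significant.

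The safety outputs are in Section 10. For the expansion cohort, 10.1.2 says "the number and description of adverse events by grade will also be reported", and 10.4.3 repeats this. For dose escalation, 10.4.4 plans "reporting toxicities by grade and type at each dose level in addition to DLTs". Nothing in 10.4 describes a summary of safety laboratory values, worst laboratory grade or change from baseline.

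The Study Calendar (3.4) schedules the main laboratory panels on days 3, 6 and 8 of every cycle, with further draws on days 1, 15 and 21 of cycle 1 and at the safety visit. Urine albumin and creatinine are measured in cycle 1.

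Laboratory findings are part of the drug's known profile. Section 12.1.2.5 says "LMB-100 administration may cause renal toxicity characterized by increased creatinine, BUN, and proteinuria", and Table 12 in 3.3.1 says "In the event of Grade 2 or greater renal toxicity hold LMB-100 administration until recovery to Grade 1 or better".

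**The concern.** The safety results can contain only what the recording rule lets into the AE record, plus the DLTs. The rule turns on symptoms, treatment, seriousness and judgement, not on measured grade. A change that CTCAE would grade can fail all five conditions and then appear in no planned output, although the value is in the database.

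This matters because safety and tolerability are the primary objective of dose escalation (1.1.1). Section 10.2 also allows the expansion dose to be set below the MTD if chronic toxicity is judged intolerable, so changes below DLT level and across cycles bear on that choice. Kidney dysfunction set the single-agent MTD (1.2.8.2.1), and mouse data in 1.2.10 suggest that tofacitinib prolongs immunotoxin exposure. A reader of the trial report would want the laboratory trend itself, not only the part that met a recording condition.

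**Working it through.** The plan gives no figure to reproduce here. The check is to follow types of laboratory change through the rules, and then to see what Table 4 says about size.

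**Step 1. Do 6.1 and 8.1.1 agree?** Section 8.1.1 counts an abnormal laboratory finding as a possible AE with no further condition. Section 6.1 admits it only under five conditions. Section 8.2 refers to 6.1 for the recording timeframe but does not say which definition governs laboratory values.

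**Step 2. Which changes reach the results?**

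| Laboratory change | DLT under 3.1.1? | AE under 6.1? |
|---|---|---|
| Grade 4 liver test, cycle 1 | Yes | Not needed to reach the results |
| Asymptomatic drug-related grade 3 liver test lasting under 7 days, not Hy's Law, cycle 1 | No, exempt | Only if treated or judged important |
| Other asymptomatic grade 3 value (not creatinine) judged not clinically significant, cycle 1 | No, exempt | Unlikely unless treated, because nearly the same judgement decides both |
| Grade 2 creatinine rise with LMB-100 held | Only at the investigator's discretion | Only if treated (for example with hydration) or judged important; the hold is not a condition |
| Kidney event that prolongs hospitalization | Depends on grade or discretion | Yes |
| Asymptomatic graded change in cycle 2 or 3 | No, the window is the first 21 days | Only if treated or judged important |

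The DLT rules therefore close part of the gap, but not for exempted grade 3 values and not after cycle 1. Section 3.3.2 likewise ties changes in tofacitinib dose to lymphopenia, neutropenia, anemia and renal or hepatic impairment. None of those actions is itself a recording condition in 6.1.

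**Step 3. How large could the under-count be?** Table 4 (13 patients, events attributed to LMB-100) gives hypoalbuminemia 9/13 = 69%, hyponatremia 3/13 = 23%, and creatinine increase, AST increase and proteinuria 2/13 = 15% each. The total is 9 + 3 + 2 + 2 + 2 = 18 findings.

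- *Overlap with a clinical sign.* Peripheral edema occurred in 1 of 1 patients at 65 mcg/kg, 3 of 3 at 100, 2 of 4 at 170 and 4 of 4 at 250. Hypoalbuminemia occurred in 1, 3, 2 and 3 at those levels. Every patient at 65, 100 and 250 had edema, so at least 1 + 3 + 3 = 7 of the 9 hypoalbuminemia patients also had edema. At 170 the minimum overlap is 2 + 2 − 4 = 0. If edema counts as an associated sign under 6.1, between 7/13 = 54% and 9/13 = 69% would be recorded.
- *Dose.* At 250 there were 3 + 3 + 2 + 2 + 1 = 11 findings (hypoalbuminemia, hyponatremia, creatinine, AST, proteinuria). At 170 there were 2 + 1 = 3 (hypoalbuminemia, proteinuria). So 14 of 18 arose above this trial's top level of 140 mcg/kg (Table 8). The other 4 were hypoalbuminemia at 65 and 100, all in patients with edema.

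Table 4 does not give timing, treatment or symptoms for each finding, so no share of droppable findings can be derived from it.

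**The case against.** The strongest reply is that the events that matter are caught elsewhere, and much of this stands. Table 12 requires the component symptoms of grade 1–3 capillary leak to be recorded individually, and 12.1.2.4 counts hypoalbuminemia as a feature of that syndrome. The kidney dysfunction in 1.2.8.2.1 prolonged hospitalization, so similar events would meet the SAE condition. Grade 3 or higher creatinine and all grade 4 liver tests fall under the cycle 1 DLT rules. Section 6.1 asks for the action taken with the test drug when a result is clinically significant, and a mandated hold is a strong candidate for that judgement. In an earlier LMB-100 study a transient grade 2 creatinine rise with a held dose was classed as an investigator-specified DLT (1.2.8.2.3). It can also be said that toxicities in 10.4.4 could include grades computed from laboratory data, but the section does not say so.

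A reader might infer more than the documents support:

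- *That known laboratory toxicities will be under-reported as a matter of course.* The rule permits an under-count. Whether one occurs depends on investigator judgement, and it could be nil.
- *That reported hypoalbuminemia would fall to 35% or less*, by assuming that half or more of the 9 cases had no sign or treatment (4.5/13 = 35%). The edema overlap in Table 4 points the other way.
- *That 17 of the 18 findings are at risk because only one, a hyponatremia, is listed as grade 3 or 4 in Table 3.* The 6.1 conditions do not depend on grade, so a finding below grade 3 is not thereby droppable.
- *That rates would look lower than in the earlier study because of this rule.* That study's recording rule is not given, and Section 10 plans no such comparison.

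What the reply does not remove is the missing grade criterion, the missing criterion for a change of study drug, the DLT exemptions, the limit to cycle 1, and the lack of any laboratory summary.

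**Conclusion.** The concern holds in a limited form. As written, graded laboratory changes that are asymptomatic, untreated and not judged important may be absent from both the AE tables and the DLT listing. They can include grade 3 values exempted from DLT and changes in later cycles. The direction is a possible under-count. Its size depends on how investigators apply the judgement and intervention conditions, which the documents do not settle, and it could be small. The conclusion rests on reading Section 10 as the full set of planned safety outputs. The point is worth correcting because the values are already collected and safety is the primary objective of dose escalation, not because a large bias has been shown.

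**What to change.** 1. In 10.4.3 and 10.4.4, add a shift table from baseline to worst CTCAE v5 grade for all treated patients, by dose level and cycle, computed from the scheduled laboratory values whether or not an AE was recorded. Cover creatinine, albumin, sodium, AST, ALT, bilirubin, CK and blood counts. Summarize the cycle 1 urine albumin and creatinine alongside it. Note under the table that cycle 1 has extra draws on days 1, 15 and 21, so worst grades are not sampled equally across cycles.
2. In 6.1, add one recording criterion: the abnormality led to a hold, delay, reduction or omission of either study drug. This changes what is recorded, not how patients are managed.
3. Reconcile 6.1 with 8.1.1 by stating which definition governs laboratory findings.

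The cost is one programmed table and short text changes, with no new sample or visit. The downside is that reported laboratory toxicity rates may look higher.

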6.2 DATA SHARING PLANS

6.2.1 Human Data Sharing Plan

What data will be shared?

I will share human data generated in this research for future research as follows:

- Coded, linked data in an NIH-funded or approved public repository.
- Coded, linked data in BTRIS (automatic for activities in the Clinical Center)
- Identified or coded, linked data with approved outside collaborators under appropriate agreements.

How and where will the data be shared?

Data will be shared through:

- An NIH-funded or approved public repository: cliniclatrials.gov
- BTRIS (automatic for activities in the Clinical Center)
- Approved outside collaborators under appropriate individual agreements.
- Publication and/or public presentations.

When will the data be shared?

- Before publication.
- At the time of publication or shortly thereafter.

6.2.2 Genomic Data Sharing Plan

No large scale genomic data will be generated on this study; therefore, the NIH GDS policy does not apply.

6.3 **RESPONSE CRITERIA**

For the purposes of this study, patients should be re-evaluated for response every 6 weeks. In addition to a baseline scan, confirmatory scans should also be obtained no less than 4 weeks following initial documentation of objective response.

Abbreviated Title: LMB100 + *tofacitinib in PDA Version Date:* 08/19/20

Response and progression will be evaluated in this study using the new international criteria proposed by the revised Response Evaluation Criteria in Solid Tumors (RECIST) guideline (version 1.1).(38) Changes in the largest diameter (unidimensional measurement) of the tumor lesions and the shortest diameter in the case of malignant lymph nodes are used in the RECIST criteria.

For pleural mesothelioma, modified RECIST for MPM (malignant pleural mesothelioma)($\underline{39}$) should be used as described in Section 6.3.9.

6.3.1 Disease Parameters

Measurable disease: Measurable lesions are defined as those that can be accurately measured in at least one dimension (longest diameter to be recorded) as:

- By chest x-ray: ≥ 20 mm;
- By CT scan:
 - Scan slice thickness 5 mm or under: as ≥ 10 mm
 - Scan slice thickness >5 mm: double the slice thickness
- With calipers on clinical exam: ≥ 10 mm.

All tumor measurements must be recorded in millimeters (or decimal fractions of centimeters).

Malignant lymph nodes. To be considered pathologically enlarged and measurable, a lymph node must be ≥ 15 mm in short axis when assessed by CT scan (CT scan slice thickness recommended to be no greater than 5 mm). At baseline and in follow-up, only the short axis will be measured and followed.

Non-measurable disease. All other lesions (or sites of disease), including small lesions (longest diameter <10 mm or pathological lymph nodes with \geq 10 to <15 mm short axis), are considered non-measurable disease. Bone lesions, leptomeningeal disease, ascites, pleural/pericardial effusions, lymphangitis cutis/pulmonitis, inflammatory breast disease, and abdominal masses (not followed by CT or MRI), are considered as non-measurable.

Note: Cystic lesions that meet the criteria for radiographically defined simple cysts should not be considered as malignant lesions (neither measurable nor non-measurable) since they are, by definition, simple cysts.

'Cystic lesions' thought to represent cystic metastases can be considered as measurable lesions, if they meet the definition of measurability described above. However, if non-cystic lesions are present in the same patient, these are preferred for selection as target lesions.

Target lesions. All measurable lesions up to a maximum of 2 lesions per organ and 5 lesions in total, representative of all involved organs, should be identified as **target lesions** and recorded and measured at baseline. Target lesions should be selected on the basis of their size (lesions with the longest diameter), be representative of all involved organs, but in addition should be those that lend themselves to reproducible repeated measurements. It may be the case that, on occasion, the largest lesion does not lend itself to reproducible measurement in which circumstance the next largest lesion which can be measured reproducibly should be selected. A sum of the diameters (longest for non-nodal lesions, short axis for nodal lesions) for all target lesions will be calculated

and reported as the baseline sum diameters. If lymph nodes are to be included in the sum, then only the short axis is added into the sum. The baseline sum diameters will be used as reference to further characterize any objective tumor regression in the measurable dimension of the disease.

Non-target lesions. All other lesions (or sites of disease) including any measurable lesions over and above the 5 target lesions should be identified as **non-target lesions** and should also be recorded at baseline. Measurements of these lesions are not required, but the presence, absence, or in rare cases unequivocal progression of each should be noted throughout follow-up.

